7.2.1 Duration/Study Day/Time

There are two reference start dates, one for the index injection and one for the repeat injection. Study day will appear in every listing where an assessment date or event date appears.

Study Day for assessments during the treatment period will be calculated for each treatment period using the dosing day for each period as the reference start date (that is, days during the T1 period should be calculated from Index dosing time, and days during T2 period should be calculated from repeat dosing time) and will be used to show start/stop day of assessments and events.

- Therefore, if the date of the assessment/event is on or after the reference date then:

$$\text{Study Day} = (\text{date of assessment/event} - \text{reference date}) + 1.$$

Study day for assessments prior to start of treatment will use the index injection date as the reference date.

- Therefore, if the date of the assessment/event is prior to the reference date then:
Study Day = (date of assessment/event – reference date).

7.2.2 Conventions for Missing and Partial Dates

All rules explained below for partial/missing dates will be followed unless contradicted by any other data recorded on the electronic Case Report Form (eCRF).

All dates presented in the individual subject listings will be as recorded on the eCRF (i.e., not completed as per the below rules).

7.2.3 Missing/Partial Start/Stop Date of Adverse Events and Concomitant Medications

Missing and partial start and stop date will be imputed for analysis purposes as follows

Partial or missing stop date will be imputed as follows:

If the stop date is completely missing and the event has resolved or the subject has stopped taking the concomitant medication, the stop date will be imputed as the date of the subject's last clinic visit in the study.

- If only the year is known, the stop date will be imputed as "31-Dec" of that year or as the date of the subject's last clinic visit in the study if in the same year.
- If the month and year are known, the stop date will be imputed as the last day of that month unless the stop date corresponds to the same month as the subject's last clinic visit in which case the date of subject's last clinic visit in the study will be used instead.

Missing start date will be imputed as follows:

- If the stop date occurs on or after the start of study drug or the event/concomitant medication is ongoing, the start date will be imputed as the date of the first dose of study drug.
- If the stop date occurs before the start of study drug, the start date of the event/concomitant medication will be imputed as the subject's screening date or the stop date of the event/concomitant medication whichever the earlier.

Partial start date (year present, but month and day missing)

- If the stop date occurs on or after the start of study drug or the event/concomitant medication is ongoing, and the year is the same as the year of first dosing the start date will be imputed as "01-Jan" of the same year or the date of the first dose of study drug

whichever is latest. If the year is different from the year of first dosing “01-Jan” will be used.

- If the stop date occurs before the start of study drug, the start date of the event/concomitant medication will be imputed as the “01-Jan” of the same year.

Partial start date (month and year present, but day missing)

- If the stop date occurs on or after the start of study drug or the event/concomitant medication is ongoing, the start date will be imputed as the first day of the same month and year unless this partial start date is in same month as the first dose of study drug in which case the date of first dose of study drug will be used.
- If the stop date occurs before the start of study drug, the start date will be imputed as the first day of the month and year of the partial stop date.

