7.12.1 Adverse Events

All AEs will be coded using the most current version of MedDRA. TEAEs and SAEs will be summarized descriptively for each treatment period.

A treatment emergent adverse event (TEAE) phase is defined as meeting either of the following 2 criteria:

- Any AE that has an onset on or after the index injection and within (after) 30 days of the last study treatment.
- Any pre-existing AE that has worsened in severity on or after the index injection and within (after) + 30 days of the last injection.

TEAEs for each treatment period, will be assessed as follows:

- A TEAE will be assigned to the treatment received immediately before onset.
- If the severity of a TEAE increases in a later period the TEAE at the increased severity will be assigned to the treatment received immediately before the increase in severity.

Onset date of adverse events on or post visit 3 but before visit 11 were considered as occurring during T1; otherwise onset date of adverse events on or post visit 11 were considered as occurring during T2

A treatment-related AE is defined as an AE as being possibly, probably or related to the study drug. If an AE has missing relationship it is assumed to be related to the study drug for analysis purposes.

Severity is classified as mild/moderate/severe/life-threatening/death (last two grades applied for SAE). If a subject reports AEs more than once within a SOC/PT, the AE with the worst-case severity will be used in the corresponding severity summaries. TEAE summary tables (except the overall summary table) will be presented by severity and overall.

The following tables will be presented by severity and overall for AEs:

- Overall incidence and the number of AEs, SAEs, TEAEs leading to withdrawal.
- Treatment-Emergent Adverse Event by System Organ Class and Preferred Term
- Related Treatment-Emergent Adverse Event by System Organ Class and Preferred Term
- Serious Treatment-Emergent Adverse Events by System Organ Class and Preferred Term
- Serious Treatment Related Treatment-Emergent Adverse Events by System Organ Class and Preferred Term
- Treatment Discontinued Treatment-Emergent Adverse Events by System Organ Class and Preferred Term
- Summary of Treatment-Emergent Adverse Events Leading to Death

All AEs will be listed.

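### Incomplete AE and medication start dates are never imputed to the repeat injection, so some post-T2 events would be tabulated under T1 and repeat-dose AE incidence understated

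*SAP*

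**What the plan says.** SAP 7.2.1 recognises that each subject can have two anchors: "There are two reference start dates, one for the index injection and one for the repeat injection". SAP 7.2.3 uses only the first of them. For an event or medication that is ongoing or stopped on or after the first dose:

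- Start date completely missing: "the start date will be imputed as the date of the first dose of study drug".
- Day missing: "the start date will be imputed as the first day of the same month and year". If T1 was given in that month, the T1 date is taken instead.
- Only the year known: the later of 01-Jan and the first dose if the year is that of first dosing, otherwise 01-Jan.

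SAP 7.2.2 adds one general exception (the rules "will be followed unless contradicted by any other data recorded on the electronic Case Report Form (eCRF"). It also keeps the listings on the dates as recorded, without imputation.

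Period assignment then depends on the onset date. SAP 7.12.1 states: "A TEAE will be assigned to the treatment received immediately before onset". It also sets a visit cut-off: "Onset date of adverse events on or post visit 3 but before visit 11 were considered as occurring during T1", with onset at Visit 11 or later going to T2. SAP 7.10 assigns medications by onset date relative to the repeat injection, and counts a medication in both periods if it was taken in both.

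TEAEs are summarised descriptively by treatment period. SAP 7.3 adds an overall column to the AE tables. The safety of single and repeat dosing is a secondary objective (SAP 3.2).

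**The concern.** Imputing a missing start to the first dose is a sensible default when the only question is whether an event is treatment-emergent, because it errs towards counting the event. This study asks a second question: which injection did the event follow? For that question the same rule is not conservative. It pulls events that followed the repeat injection back into the index period, and nothing in 7.2.3 can move an event forward.

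The by-period AE tables are the study's evidence on repeat-dose safety, and few subjects receive T2. A rule that can only lower the T2 count and raise the T1 count makes repeat dosing look better tolerated than it was.

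**Working it through.** The documents give no figure on this point and no power calculation, so there is nothing to reproduce. The check applies 7.2.3 and then the assignment rules of 7.12.1, before any eCRF override.

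**Inputs**
- 28-day follow-up after each injection, with injections 4 to 8 weeks apart (Protocol 3.1).
- Baseline on Day 0 and injection on Day 1 (Protocol 3.1). Visit 11 is T2 Day 0 (Protocol 3.5.5.5).
- 12 subjects completing both injections (SAP 5).
- Assumptions: T2 falls evenly on days d = 1 to 30 of a 30-day month, Visit 11 is the day before T2, and onset is uniform over the window considered.

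**1. Direction.** For an event that began on or after T1, the imputed date (T1 date, 01-Jan or first of the month) is never later than the true onset. A true T1 event therefore cannot be moved to T2, but a true T2 event can be moved to T1.

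**2. Start date fully missing.** The imputed date is the T1 date, so every such post-T2 event goes to T1.

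**3. Day missing.** The imputed date is the first of the onset month (or the T1 date, if T1 was in that month). The event moves to T1 if its onset is in T2's calendar month and the imputed date precedes Visit 11.

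- Share of the 28 days in T2's own month: min(28, 31 − d)/28. Summed over d: 3 + (27 + 26 + … + 1)/28 = 3 + 13.5 = 16.5. Mean: 16.5/30 = 55%.
- Share of the first 7 days: min(7, 31 − d)/7. Summed: 24 + (6 + 5 + … + 1)/7 = 24 + 3 = 27. Mean: 27/30 = 90%.
- If T2 is on the 1st, the imputed date is the T2 date. If T2 is on the 2nd, it is the Visit 11 date. Both are assigned to T2, and each contributes 1 to both sums.
- Moved to T1: (16.5 − 2)/30 = **48%** of the 28 days, and (27 − 2)/30 = **83%** of the first week.
- If the treatment-before-onset sentence governs instead of the Visit 11 cut-off, only d = 1 escapes: (16.5 − 1)/30 = 52% and (27 − 1)/30 = 87%.

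**4. Simulation check.** The rules were coded with the Visit 11 cut-off, T1 uniform over a year, gaps of 28 to 56 days and 60,000 subjects per scenario. Share of post-T2 events moved to T1:

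| Start date | Uniform onset | Front-loaded onset (exponential, mean 5 days) |
|---|---|---|
| Fully missing | 100% | 100% |
| Year only | 96% | 98% |
| Day missing | 49% | 79% |

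The share of T1 events moved to T2 was 0% throughout. Fixing the gap at 28 or 56 days changed little.

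**5. Effect on the tables.** One subject in 12 is 1/12 = 8.3 percentage points of T2 incidence, provided that subject has no other T2 event of the same kind. As an illustration, take equal true AE counts in both periods, a fraction m with incomplete dates, and a fraction v of those moved from T2. The apparent T2/T1 ratio is (1 − mv)/(1 + mv).
- m = 5%: 0.95 (v = 50%) to 0.90 (v = 100%).
- m = 10%: 0.90 to 0.82.
- m = 20%: 0.82 to 0.67.

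The true ratio is 1.00 in each case. The documents give no value for m.

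**6. Medications.** A medication begun after T2 with no start date is given a T1 onset. Because SAP 7.10 counts a medication in both periods if taken in both, the likely result is a spurious T1 entry rather than a lost T2 entry.

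**The case against.** The strongest reply is the SAP 7.2.2 exception. A known stop date or other eCRF entries may show that a T1 onset is impossible, and the rule then gives way. This stands in part: it is wrong to say that every post-T2 event with a missing start date must end up in T1. But first reporting an event after T2 does not in itself contradict an earlier start. The AE items listed in Protocol section 4 include neither the visit of first report nor the treatment period, and the SAP names no item to consult. The exception may rescue some events, but not reliably.

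Second, the trigger should be rare. Start date is a collected AE item, omissions are queried (Protocol 5.1), data are entered directly at visits (Protocol 5.2.2), and visits are frequent after T2. This stands and limits the likely size.

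Third, the tables are descriptive, no decision hangs on them, the overall column does not change, and listings show the recorded dates. All true. A careful reader could find the affected events in the listings, but not from the by-period tables.

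Finally, the Visit 11 cut-off counts an AE that starts on T2 Day 0, before the injection, as a T2 event. That works slightly the other way, but it is separate from the imputation and does not offset it in any planned manner.

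**Conclusion.** The concern holds. As written, the imputation rules can move post-T2 AEs into T1 and never the reverse, so any error understates repeat-dose incidence in the by-period tables. Absent contradicting eCRF data, this affects all fully missing start dates. It also affects day-missing dates whose onset falls in about 48% of the T2 follow-up, or about 83% of its first week. Those two figures rest on T2 being spread evenly over a 30-day month and Visit 11 being the day before T2.

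Two stronger readings should be resisted. A reader might infer that 55% of the follow-up and 90% of the first week are misassigned, since that much falls in T2's own month; this ignores T2 given on the 1st and the Visit 11 cut-off. A reader might also infer that the repeat-dose safety results will be materially biased. The documents do not support that: the number of incomplete dates is unknown and probably small, and no test or decision rule uses these tables. The case for changing the rule is that its error has one direction, each subject weighs about 8 points, and correction is cheap.

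**What to change.** Amend SAP 7.2.3 before database lock:

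1. Keep the present rule for events that stopped before the first dose.
2. For other events in subjects who received T2, impute the T2 injection date if (a) the known parts of the start date and the stop date allow onset on or after T2, and (b) no eCRF record shows the event present before T2. Name the records to be used, for example eCRF entry date or visit notes, since the listed AE items do not include one.
3. Otherwise keep the present rules.
4. Never impute outside the known month or year. With T2 on 20 April, an AE dated only to April becomes 20 April unless a record shows it earlier; one dated only to May stays at 1 May.
5. Apply the same rule to concomitant medications.
6. Footnote AEs with incomplete onset dates and show the by-period counts under both the present and the revised allocation.

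The cost is SAP wording and a few lines of code; no study procedure changes. The drawback is that a few late-reported T1 events may be counted under T2. That is conservative for repeat dosing, and the two-allocation display makes it visible.

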7.2.4 Electrocardiogram Data

For ECG data recorded on continuous scales, if more than one value is recorded at a time point, the mean value rounded to the integer will be presented. For overall interpretation if more than one value is recorded, the most severe (worst case) of the respective readings will be taken.

7.2.5 Unscheduled Visits

Except for ET assessments, only scheduled post-baseline laboratory and vital signs values will be tabulated. Post-baseline repeat/unscheduled assessments will be disregarded, although these post-baseline assessments will be listed in the relevant appendices to the CSR.

For post-baseline PD, laboratory and vital sign data, if an Early Termination assessment falls between two visits and the visit prior to that ET visit has a valid assessment, then that ET assessment will be mapped to the subsequent visit within the treatment period. If the scheduled assessment prior to an ET assessment is missing, then the ET assessment will be mapped to that prior assessment. Assessments from T1 cannot be assigned to T2.

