3.5.5.5 Laboratory Parameters

The following clinical laboratory tests are to be performed at Screening, Baseline, T1 – Day 5, T1 – Day 28, T2 – Day 5, and T2 – Day 28 (Visit 19/EOS/ET) unless noted below:

Hematology: Hemoglobin, hematocrit, red blood cell count, WBC count (with differential [lymphocytes, neutrophils, eosinophils, basophils, and monocytes]), and platelet count.

Serum Chemistry: albumin, alkaline phosphatase, AST, ALT, direct bilirubin, total bilirubin, blood urea nitrogen, calcium, chloride, creatine kinase (Screening only), creatinine, gamma-glutamyl transferase, glucose, lactate dehydrogenase, potassium, sodium, and uric acid.

Other tests: HbA1c, HIV, hepatitis B, and hepatitis C at Screening. Coagulation tests at Screening or Baseline: activated PTT, PT, and INR. Coagulation tests may be repeated prior to the index and repeat injection, if deemed necessary by the Investigator.

Urinalysis: Dipstick analysis: color, turbidity, specific gravity, pH, glucose, protein, ketones, urobilinogen, bilirubin, blood nitrate, leukocyte esterase, and microscopic examination when indicated by dipstick results.

Urine drug screen: Includes opiates, barbiturates, benzodiazepines, tricyclic antidepressants, cannabinoids, PCP, cocaine, ecstasy, and amphetamines. A urine drug screen will be obtained at Screening, Baseline, and T1 – Day 28. A urine drug screen may be repeated if deemed necessary by the Investigator.

WOCBP: Serum pregnancy test at Screening. Urine pregnancy test at Baseline and at Visit 11 (T2 – Day 0). A urine pregnancy test may be repeated if deemed necessary by the Investigator.

Laboratory samples will be analyzed by the local laboratory. In the event of an unexplained clinically noteworthy abnormal laboratory test value, the test should be repeated immediately and followed up until it has returned to the normal range and/or an adequate explanation of the abnormality is found.

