5.2.8.2 Laboratory Data

Mean changes from Baseline at each post-baseline time point for each laboratory variable will be presented. In addition, each reading will be classified as below, within, or above normal range, based on ranges supplied by the laboratory used. Shift tables for the Baseline and follow-up measurements will be presented.

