7.2 Baseline

Unless otherwise specified, baseline is defined as the last non-missing measurement taken prior to treatments T1 or T2 (reference start date). This includes screening or unscheduled assessments that would have been performed no earlier than 21 days before the reference start date.

In the case where the last non-missing measurement and the reference start date coincide, that measurement will be considered pre-reference, but AEs and medications commencing on the reference start date will be considered post-reference.

For laboratory tests, baseline is defined as the last measurement obtained during screening prior to T1.

For vital signs parameters, an assessment performed on reference start date with time point marked as “pre-dose” will be considered as baseline for the given treatment period.

Baseline ECG is the last measurement prior to the index injection.

For physical exams, baseline is defined as the last assessment prior to T1 on Day 0.

For General and Targeted Neurological Exam baseline for each treatment period is defined as the pre-dose assessment.

For cortisol suppression, glucose, and white blood cell counts, baseline is defined as the last non-missing value obtained prior to T1 or T2, which is T1/T2 Day 1 pre-dose measurement.

For NPRS and BPI-SF, baseline is defined as the last non-missing value obtained prior to T1 or T2, which is T1/T2 Day 0 measurement.

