7.12.2 Laboratory Data

Descriptive statistics of the observed values and change from baseline (continuous data) will be presented by treatment period and visit (Screening, T1 – Day 5, T1 – Day 28, T2 – Day 5, and T2 – Day 28 (Visit 19/EOS/ET)) for each hematology (Hemoglobin, hematocrit, red blood cell count, WBC count (with differential [lymphocytes, neutrophils, eosinophils, basophils, and monocytes]), and platelet count), serum chemistry (albumin, alkaline phosphatase, AST, ALT, direct bilirubin, total bilirubin, blood urea nitrogen, calcium, chloride, creatine kinase (Screening only), creatinine, gamma-glutamyl transferase, glucose, lactate dehydrogenase, potassium, sodium, and uric acid), and urinalysis (Dipstick analysis: color, turbidity, specific gravity, pH, glucose, protein, ketones, urobilinogen, bilirubin, blood nitrate, leukocyte esterase, and microscopic examination when

indicated by dipstick results) parameter. Each measurement (continuous data) will be classed as below, within, or above normal range, based on ranges supplied by the laboratory used. Shift tables in relation to the normal range from baseline to each follow-up visit will be presented.

The following lab parameters will be listed only. HbA1c, HIV, hepatitis B, and hepatitis C at Screening. Coagulation tests at Screening or Baseline: activated PTT, PT, INR, serum pregnancy test at Screening, urine pregnancy test at Baseline and at Visit 11 (T2 – Day 0), and MRI.

A listing of any clinically significant laboratory measurements recorded throughout the study will be presented.

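### Repeat and unscheduled post-baseline laboratory and vital-sign values are left out of the safety tables, and no worst-value summary is described that would count what they show

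*SAP*

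**What the plan says.** SAP 7.2.5 sets the rule for both data types: "Except for ET assessments, only scheduled post-baseline laboratory and vital signs values will be tabulated". It continues: "Post-baseline repeat/unscheduled assessments will be disregarded, although these post-baseline assessments will be listed in the relevant appendices to the CSR".

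The classification rules are worded more broadly. Protocol 5.2.8.2 says "each reading will be classified as below, within, or above normal range, based on ranges supplied by the laboratory used", and SAP 7.12.2 says "Each measurement (continuous data) will be classed as below, within, or above normal range". Neither is confined to scheduled draws. SAP 7.12.2 builds its shift tables from baseline to each follow-up visit. SAP 7.12.3 counts vital signs in clinical-concern categories (systolic pressure at or above 160 mmHg, diastolic at or above 100 mmHg, heart rate below 60 or above 100 bpm).

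Protocol 3.5.5.5 generates repeat laboratory values by design. After an unexplained noteworthy abnormal result, "the test should be repeated immediately and followed up until it has returned to the normal range" or an adequate explanation is found.

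**The concern.** Safety and tolerability are a secondary objective, and the shift tables and concern counts are where a reader will look for how many subjects went out of range. Between scheduled visits, an unscheduled assessment may be the only record of an excursion. If such values are always dropped, a count of subjects with an abnormal value can be too low.

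The SAP takes the worst case elsewhere: for the overall ECG interpretation (7.2.4) and for adverse event severity (7.12.1). It describes no counterpart for laboratory values or vital signs. On Day 1, the vital signs taken during and after the injection are summarized as means (7.12.3).

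**Working it through.** The plan states no figure on this point, so there is none to reproduce. The check compares the texts, works out the gaps in the schedule, and then sizes one omitted subject.

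**1. Which rule governs the tables.** Protocol 5.2.8.2 covers every reading and SAP 7.12.2 every measurement. SAP 7.2.5 limits tabulation to scheduled and early-termination values. Read together, an unscheduled value could be classified but not tabulated. The readable part of SAP section 10 does not list this as a change from the protocol.

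**2. What is lost, case by case.**
- Scheduled value abnormal, repeat normal: the abnormal value stays in the table and nothing is lost.
- Scheduled value abnormal, repeat worse in the same direction: the below/within/above class does not move, but the more extreme value is missing from the summaries.
- Scheduled value not abnormal, unscheduled value abnormal: not counted. The same holds when a scheduled systolic pressure is below 160 mmHg and an unscheduled one reaches it.
- Abnormality found and followed only at unscheduled assessments: none of it is counted.

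**3. Direction.** The set of all post-dose values contains the set of scheduled and early-termination values. A subject who is ever abnormal on the smaller set is therefore ever abnormal on the larger one. Using all values can raise a count of subjects ever abnormal or leave it unchanged, but cannot lower it. This does not hold for by-visit tables, where a repeat could replace an abnormal scheduled value with a normal one.

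**4. Gaps in the schedule.**
- Chemistry, hematology and urinalysis (SAP 7.12.2): post-dose panels on Days 5 and 28 of each period; 28 − 5 = 23 days.
- Vital signs (SAP 7.12.3): Days 0, 1, 2, 3, 4, 5, 8, 15 and 28; longest nominal gap 28 − 15 = 13 days.
- Glucose and WBC (Protocol 3.5.4.2 and 3.5.4.3, SAP 7.11.1): Days 1 to 5, 8, 15 and 28; longest nominal gap again 13 days. The additional days feed the pharmacodynamic summaries; the shift tables still use Days 5 and 28.

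**5. Weight of one subject.** SAP section 5 enrolls until 12 subjects have received both injections. In T2, 1/12 = 8.3 percentage points. In T1 the share is 1/N with N the number dosed, so it is smaller if N exceeds 12.

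**6. Illustration.** Let q be the chance that a subject has an abnormality seen only at an unscheduled assessment. The documents do not give q, so these values are assumed. The chance that at least one of 12 is omitted is 1 − (1 − q)^12, and the expected number is 12q.

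| Assumed q | Chance of at least one omitted | Expected number omitted |
|---|---|---|
| 1% | 11% | 0.12 |
| 2% | 22% | 0.24 |
| 5% | 46% | 0.60 |
| 10% | 72% | 1.2 |
| 20% | 93% | 2.4 |

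**The case against.** The strongest reply is that important values already have a route into a table. Under Protocol 4.1.4, a new or worsened laboratory abnormality is recorded as an adverse event if it meets any one of four criteria, clinical significance in the investigator's judgment among them, and nothing limits this to scheduled draws. Adverse events with onset after the injection enter the treatment-emergent tables (SAP 7.12.1). Early-termination values are tabulated, unscheduled values are listed, and SAP 7.12.2 lists clinically significant laboratory results from the whole study. With about 12 subjects, listings can be read in full.

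This stands, and it limits the point. A reader might infer that unscheduled values cannot enter the safety summaries at all, and the documents do not support that. The route is still partial. An out-of-range laboratory value meeting none of the four criteria reaches no table. Protocol 4.1.4 covers laboratory values only, so an unscheduled vital-sign excursion is tabulated only if reported under the general adverse event definition (Protocol 4.1.1), and even then it does not enter the concern count.

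A second reply is that protocol-driven repeats follow an abnormal value already obtained. Where that value was scheduled, it remains tabulated. This also stands: the dropped values are not shown to be the ones most likely to matter.

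Third, scheduled-only data suit by-visit tables. That is correct, and the fix leaves those tables alone. The SAP's list of tables is blacked out, so the statement here is only that the readable text describes no worst-value display.

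**Conclusion.** The gap is real and modest. SAP 7.2.5 is narrower than Protocol 5.2.8.2 and SAP 7.12.2. With no worst-post-dose summary described, an abnormality first seen, or worsening, at an unscheduled assessment is not counted in the laboratory shift tables or the vital-sign concern counts. Any error in a count of subjects ever abnormal is toward too few. Each omitted subject is 8.3 percentage points of 12 in T2. How many would be omitted depends on a rate the documents do not give.

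Two further readings are not supported. One is that unscheduled values may set the baseline but never count as outcomes. The sentence "This includes screening or unscheduled assessments that would have been performed no earlier than 21 days before the reference start date" belongs to a default that yields to specific rules, and SAP 7.2 gives one for each data type. For laboratory data, "For laboratory tests, baseline is defined as the last measurement obtained during screening prior to T1". The vital-sign rule begins "For vital signs parameters, an assessment performed on reference start date with time point marked as" and goes on to require the pre-dose label. What remains unclear is whether a repeat draw during screening may be the laboratory baseline. The other is that the 23-day gap applies throughout; it does not describe the measurement schedule for vital signs, glucose or WBC.

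**What to change.** - **SAP 7.2.5:** keep by-visit summaries on scheduled and early-termination values, and state that this restriction does not apply to the worst-value outputs below.
- **SAP 7.12.2:** add a laboratory shift table from baseline to worst post-dose value for each treatment period, using all scheduled, repeat, unscheduled and early-termination values.
- **SAP 7.12.3:** derive the clinical-concern counts per period from the same full set of post-dose values, and say whether Day 1 readings enter individually or as means.
- **Period window:** state which period holds a value taken after T1 Day 28 and before the repeat injection.
- **Reconciliation:** align SAP 7.2.5 with SAP 7.12.2 and Protocol 5.2.8.2, record any intended narrowing in SAP section 10, and state whether a screening repeat may be the laboratory baseline.

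The cost is SAP wording and one extra shift table per laboratory panel. No new data are needed, because the values are already collected and listed. Slightly more abnormal values may be tabulated.
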